7 STATISTICAL ANALYSES

All analyses will be performed in SAS using version 9.2 or higher.

7.1 General Methods

Continuous variables will be summarized using descriptive statistics, i.e., medians, minimums, maximums, and means with standard deviations of the mean and quartiles. Categorical variables will be summarized by frequencies and percentages. Percentages will be rounded and may not always add up to 100.

Confidence intervals for binomial proportions will be derived using the Clopper-Pearson method².

Time to event distributions (i.e., progression free survival, overall survival) will be estimated using Kaplan Meier techniques. When appropriate, the median along with 95% CI will be estimated based on Brookmeyer and Crowley methodology³ (using log-log transformation for constructing the confidence intervals). Rates at fixed time points (e.g., PFS at 24 weeks) will be estimated using 95% CIs with Greenwood formula⁴.

Laboratory results, adverse events, and other symptoms will be graded using the National Cancer Institute (NCI) Common Terminology Criteria for Adverse Events (CTCAE), version 4.03, except where CTCAE grades are not available. Adverse events will be categorized using the most current version of Medical Dictionary for Regulatory Activities (MedDRA), by system organ class and preferred term.

7.2 Study Conduct

7.2.1 Study Information

Listing:

- Batch numbers

7.2.2 Accrual

Summary:

- Number (%) of subjects accrued by country and investigational site based on All Enrolled population by treatment and overall.
- Number of subjects accrued by month based on All Enrolled population.

Listing:

- Subjects accrued by country and investigational site based on All Enrolled population

7.2.3 Protocol Deviation

The following programmable deviations will be considered as relevant protocol deviations. Nonprogrammable relevant eligibility and on-treatment protocol deviations, as well as significant (both programmable and non-programmable) eligibility and on-treatment protocol deviations will be reported through ClinSIGHT listings.

Table 7.2.3- 1: Relevant Protocol Deviations

Timing	Part	Deviation Items
At entrance	All Parts	Subjects with ECOG PS > 1 Subjects without evaluable disease at baseline Subjects with absolute neutrophil count (ANC) <1500 / μ L Subjects with platelet count < 60×10^3 / μ L Subjects with hemoglobin < 8.5 g/dL Subjects with Prothrombin time (PT)-international normalized ratio (INR) > 2.3 or PT > 6 seconds above control

Timing	Part	Deviation Items
		Subjects with serum albumin < 2.8 g/dL Subjects with total bilirubin > 3 mg/dl Subjects with AST > 5 x the institutional ULN Subjects with ALT > 5 x the institutional ULN Subject with confirmed ECG QTcF > 480 msec prior to study treatment administration Subjects with a serum creatinine of $\geq 1.5 \times$ ULN and a creatinine clearance (CrCl) ≤ 40 mL/min using Cockcroft-Gault equation Subjects with co-infection of HBV and HCV or HBV and HDV Child-Pugh score of 7 points or higher Subject received <1 line of prior therapy
	Part 1, 2 and 3	
	Part 2	Subject received >2 line of prior therapy Subjects with both plasma membrane and cytoplasmic H score < 50 for GPC-3 expression in the tumor tissue
	Part 4	Subject received any prior therapy Subjects with both plasma membrane and cytoplasmic H score < 50 for GPC-3 expression in the tumor tissue
On-Study	All Parts	Subjects receiving concurrent anticancer therapy (defined as systemic therapy or any investigational drug, non-systemic therapy for HCC, chemo radiation, curative surgery, palliative radiotherapy/surgery on any target lesion) that not allowed per protocol. Subjects treated differently than as assigned (subjects who received the wrong treatment, excluding the never treated)

A summary table and a by subject listing will be produced.

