 - ii) HCV-HCC: Active or resolved HCV infection as evidenced by detectable HCV ribonucleic acid (RNA) or antibody, respectively. Subjects on antiviral therapy for hepatitis C are permitted and should continue treatment during the study up to the follow-up period. Subjects with active HCV who are not on antiviral therapy at screening cannot be enrolled in the study.
- i) At least 1 RECIST v1.1 previously untreated, unidimensionally measurable lesion by contrast-enhanced tri-phasic computed tomography (CT ≥ 10 mm or contrast-enhanced dynamic magnetic resonance imaging (MRI) scan ≥ 10 mm (malignant lymph nodes must be ≥ 15 mm on short axis) (additional details are included in Appendix 6)⁸¹
 - i) The lesion can be accurately measured unidimensionally according to RECIST v1.1
 - ii) The lesion has not been previously treated with surgery, radiotherapy, and/or locoregional therapy (eg: radiofrequency ablation, percutaneous ethanol or acetic acid injection, cryoablation, high-intensity focused ultrasound, transarterial chemoembolization, transarterial embolization, etc.)
 - iii) Previously treated lesions can be considered target lesions if there is clear evidence of progression.
 - iv) Bone metastases are not considered measurable lesions, unless there is a measurable soft tissue component per RECIST v1.1 (see Appendix 6).⁸¹
 - v) The measurable lesion cannot be biopsied during treatment (if there is only 1 lesion).
- j) For subjects who progressed after locoregional therapy, locoregional therapy for HCC must be completed at least 4 weeks prior to the baseline scan. All acute toxic effects of any prior local treatment must have resolved to NCI CTCAE v4.03 Grade ≤ 1 or been deemed irreversable.

Screening laboratory values must meet the following criteria:

- i) Adequate hematologic function:
 - (1) Neutrophils $\geq 1500/\mu L$

- (2) Platelets $\ge 60 \times 10^3/\mu L$ (transfusion to achieve this level is not permitted within 2 weeks of first study drug administration)
- (3) Hemoglobin \ge 8.5 g/dL (may be transfused to meet this requirement within 2 weeks of first study drug administration)
- (4) Prothrombin time (PT)-international normalized ratio (INR) ≤ 2.3 or PT ≤ 6 seconds above control.
- ii) Adequate hepatic function
 - (1) Albumin $\geq 2.8 \text{ g/dL}$
 - (2) Total bilirubin $\leq 3 \text{ mg/dL}$
 - (3) AST \leq 5 × the institutional ULN
 - (4) ALT \leq 5 × the institutional ULN

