iii) Adequate renal function with a serum creatinine of $< 1.5 \times ULN$ or a creatinine clearance (CrCl) > 40 mL/min using Cockcroft-Gault formula below:

Female CrCl = $(140 - age in years) \times weight in kg \times 0.85$ $72 \times serum creatinine in mg/dL$ Male CrCl = $(140 - age in years) \times weight in kg \times 1.00$ $72 \times serum creatinine in mg/dL$

- k) Ability to comply with treatment, PK and research sample collection (when indicated), and required study follow-up.
- Subject Re-enrollment: This study permits the re-enrollment of a subject that has discontinued the study as a pretreatment failure (ie, subject has not been treated). If re-enrolled, the subject must be re-consented.

3) Age and Reproductive Status

- a) Males and Females, ages 18 or age of majority
- b) Women of childbearing potential (WOCBP) must have a negative serum or urine pregnancy test (minimum sensitivity 25 IU/L or equivalent units of human chorionic gonadotropin) within 24 hours prior to the start of study drug.
- c) Women must not be breastfeeding.
- d) WOCBP must agree to follow instructions for method(s) of contraception for the duration of treatment with study drug (s) BMS-986183 monotherapy plus 5 half-lives of study drug plus 30 days (duration of ovulatory cycle) for a total of 90 days post-treatment completion (BMS-986183 dose escalation [Part 1] and BMS-986183 dose expansion [Part 2]). WOCBP must agree to follow instructions for method(s) of contraception for the duration of study treatment with nivolumab and 5 months (150 days) after the last dose of study drug (ie, 30 days [duration of ovulatory cycle] plus the time required for the study drug to undergo approximately 5 half-lives) (BMS-986183 and nivolumab dose escalation [Part 3] and BMS-986183 and nivolumab dose expansion [Part 4]).

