Nonmeasurable lesions are all other lesions, including small lesions (longest diameter < 10 mm or pathological lymph nodes with ≥ 10 to < 15 mm short axis), as well as nonmeasurable lesions. Lesions considered nonmeasurable include leptomeningeal disease, ascites, pleural or pericardial effusion, inflammatory breast disease, lymphangitic involvement of skin or lung, and abdominal masses/abdominal organomegaly identified by physical examination that is not measurable by reproducible imaging techniques.

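### The SAP's PT/INR deviation row joins two alternative entry limits with "or", so it reports eligible subjects as relevant deviations

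*SAP*

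**What the plan says.** Protocol Section 3.3.1 (Inclusion Criteria), under the screening laboratory values, asks for "Prothrombin time (PT)-international normalized ratio (INR) ≤ 2.3 or PT ≤ 6 seconds above control". Meeting either limit is enough.

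SAP Section 7.2.3 lists the programmable relevant deviations in Table 7.2.3-1 and promises a summary table and a by-subject listing. The coagulation row for all parts flags "Subjects with Prothrombin time (PT)-international normalized ratio (INR) > 2.3 or PT > 6 seconds above control".

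The renal criterion has the same structure in the protocol: serum creatinine below 1.5 × ULN "or a creatinine clearance (CrCl) > 40 mL/min using Cockcroft-Gault formula below". The SAP row for it flags creatinine at or above 1.5 × ULN "and a creatinine clearance (CrCl) ≤ 40 mL/min using Cockcroft-Gault equation".

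For disease at entry, inclusion criterion 2(i) requires "At least 1 RECIST v1.1 previously untreated, unidimensionally measurable lesion", with further terms on when a previously treated lesion may serve as a target lesion. The SAP row flags "Subjects without evaluable disease at baseline". The SAP text available does not define evaluable disease.

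**The concern.** When a criterion is met by satisfying A or B, it is breached only by failing both. The PT/INR row flags failure of either limit, so a subject who was properly enrolled on one limit is reported as an entry deviation because of the other. The deviation table is meant to tell a reader how well the eligibility rules were kept. Here it would overstate departures on coagulation, in a population that Protocol Section 4.5.3 describes as generally having underlying cirrhosis and reduced hepatic function.

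The disease row raises a lesser question in the opposite direction. If evaluable disease is taken to include nonmeasurable disease, a subject with no measurable lesion would breach the protocol without being flagged in this table.

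**Working it through.** There is no sample size, power or error rate to reproduce. The check is logical, with one illustrative calculation.

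**PT/INR row.** Let A be INR ≤ 2.3 and B be PT no more than 6 s above control (Protocol 3.3.1).

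- Protocol: eligible if A or B. Breach = not (A or B) = (not A) and (not B).
- SAP row: flagged if (not A) or (not B).

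| INR limit met | PT limit met | Eligible per protocol | SAP flag as written | Flag with "and" |
|---|---|---|---|---|
| yes | yes | yes | no | no |
| yes | no | yes | **yes (false)** | no |
| no | yes | yes | **yes (false)** | no |
| no | no | no | yes | yes |

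As written, the row is wrong in 2 of 4 combinations. Both errors fall among the 3 eligible combinations, and the one ineligible combination is caught. With the logical and, the flag is the exact complement of eligibility in 4 of 4.

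**Controls from the same table.**

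- Renal: the protocol accepts creatinine < 1.5 × ULN or CrCl > 40 mL/min; the SAP flags ≥ 1.5 × ULN and ≤ 40 mL/min. There are no mismatches in 4 combinations.
- GPC-3 (Parts 2 and 4): the protocol accepts a membrane or a cytoplasmic H score of at least 50; the SAP flags subjects in whom both are below 50. This is also correct.

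The PT/INR row is the exception, which suggests a slip rather than a deliberate rule.

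**How wide the false-flag band could be.** The documents give neither a control PT nor an ISI, so both are assumptions. Use INR = (PT / control PT)^ISI with control PT 12 s. A PT 6 s above control is 18 s, and 18/12 = 1.5.

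| Assumed ISI | INR at PT = 18 s | Eligible but flagged |
|---|---|---|
| 1.0 | 1.5 | INR above 1.5, up to 2.3 |
| 1.5 | 1.5^1.5 ≈ 1.84 | INR above 1.84, up to 2.3 |
| 2.0 | 1.5² = 2.25 | INR above 2.25, up to 2.3 |
| about 2.05 | 2.3 | none |

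The last row solves 1.5^ISI = 2.3: ISI = ln 2.3 / ln 1.5 ≈ 2.05. Varying the control PT at ISI 1.0 moves the lower edge little: 17/11 ≈ 1.55 at 11 s and 20/14 ≈ 1.43 at 14 s.

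**Disease row.** Criterion 2(i) turns on a measurable lesion. Protocol Appendix 6, Section 1.1 treats the rest as a separate class: "Nonmeasurable lesions are all other lesions, including small lesions (longest diameter < 10 mm" and others. The SAP row turns on evaluable disease. If that term means measurable disease, the row matches the core of the criterion. If it covers nonmeasurable disease, a subject with only such disease is ineligible and not flagged. The documents do not settle which is meant.

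**The case against.** **The limits may be alternatives by reporting.** A sponsor could say that the protocol's or means whichever test the site reports. The protocol's coagulation panel lists PT/INR, so both values may be available, and the row then flags an eligible subject. Where only one is reported, the objection has force against a bare logical and: a high INR with no usable PT or control value would go unflagged, replacing over-counting with under-counting. The fix therefore needs a rule for this case.

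**The band may be narrow or nearly empty.** This stands. At ISI 2.0 the band is only 2.25 to 2.3. Entry is limited to Child-Pugh scores of 6 or less, and current therapeutic anticoagulation is excluded. No frequency can be inferred.

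**Evaluable may mean measurable.** The SAP's Response Evaluable Population requires a baseline tumor measurement, which leans that way. But that population also depends on what happens after treatment, so it does not define a baseline disease status. A reader might infer that the row certainly misses protocol breaches; the documents support only the conditional statement.

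**A missing measurable lesion would show elsewhere.** This is largely right. SAP Section 7.3.3 summarises and lists the number of target lesions and the sum of their diameters at baseline, and SAP Section 7.2.3 sends significant deviations to separate listings. Neither corrects the row.

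**Response results.** Because a partial response is defined on target lesions, a reader might infer that the ORR is distorted. The documents do not support this. Neither Protocol Section 8.2 nor SAP Section 6.3 defines a population that depends on deviations, so flagging a subject, or failing to, alters no numerator, denominator or confidence interval.

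**Conclusion.** The PT/INR row is wrong as written. It contradicts the protocol criterion it is meant to check, over-flags eligible subjects and misses no true breach. This conclusion needs no assumption beyond reading both documents literally, and the correctly negated renal and H-score rows support that reading. The size is uncertain: with a control PT of 12 s, the affected INR band runs from anywhere between 1.5 and 2.25 up to 2.3 across ISI 1.0 to 2.0, and the number of subjects in it is unknown.

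The disease row is a secondary, conditional point: an undefined term stands where the protocol is specific. It leaves a gap in this table only if the term includes nonmeasurable disease.

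Both matters are confined to the relevant-deviation summary and its by-subject listing. They should be corrected because those outputs describe adherence to eligibility, not because any efficacy or safety estimate depends on them.

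**What to change.** In SAP Table 7.2.3-1:

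1. Reword the coagulation row to flag INR above 2.3 **and** PT more than 6 s above control. Add that where only one of the two is reported, the subject is flagged if that value exceeds its limit. A PT without a control value should be handled as not reported.
2. Replace the disease row with one that follows inclusion criterion 2(i) in full: no RECIST v1.1 measurable lesion at baseline that meets the protocol's terms, including those on previously untreated lesions and on treated lesions with clear progression. If some of these terms cannot be programmed, program the measurable-lesion part and assign the rest to the nonprogrammable listings.

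The cost is two table rows and their programming. No protocol change, new data collection or change to any analysis is needed, provided the control PT is already captured. The documents do not show whether it is; if not, the one-value rule applies.

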7.3 Study Population

7.3.1 Subject Disposition

Summary:

- Pre-treatment period: The number (%) of subjects of the following will be based on All Enrolled Subjects.
 - All enrolled into the study
 - Entering the treatment period, i.e. All treated subjects
 - Enrolled but not entering the treatment period together with the reasons
- End of treatment period: The number (%) of subjects of the following will be summarized by treatment and overall based on All Treated Subjects
 - All treated subjects
 - Subjects continuing in treatment period
 - Subjects not continuing in treatment period
 - Reasons for not continuing in treatment period

- Subjects continuing in the study
 - Subject continuing into the survival/response follow-up period
 - Subject continuing into the safety follow-up period
- Subject not continuing in the study
 - Reasons for not continuing in the study
 -
- End of safety follow-up: The number (%) of subjects of the following will be summarized by treatment and overall based on All Treated Subjects
 - Subjects continued into safety follow-up
 - Subject not continuing to the survival/response follow-up
 - Subject not continuing to the survival/response follow-up
 - Reasons for not continuing to the survival/response follow-up
- End of the survival/response follow-up period: The number (%) of subjects of the following will be summarized by treatment and overall, based on the All Treated Subjects.
 - Subjects continuing in the survival/response follow-up period
 - Subjects not continuing in the survival/response follow-up period
 - Reasons for not continuing in the survival/response follow-up period

Listing:

- Pre-treatment period: Subjects who discontinued from the study before treatment (for screen failures)
- End of treatment period: Treated subjects who discontinued from the study treatment with the specific reason for discontinuation.
- End of safety follow-up or survival/response follow-up: Treated subjects who discontinued from safety follow-up or survival/response follow-up with the reason for not being followed.

7.3.2 Demographics and Other Baseline Characteristics

Summary:

Descriptive statistics will be summarized for the following baseline characteristics for all treated subjects by treatment and overall. All baseline presentations will identify subjects with missing measurements.

- Age (in years); age category (< 65, ≥ 65 - < 75 , ≥ 75)
- Gender (Male, Female)

- Race (White, Black or African American, Asian (Asian Indian, Chinese, Japanese, Korean, Taiwanese, Asian Other), American Indian or Alaska Native, Native Hawaiian or Other Pacific Islander, Other)
- Ethnicity (Hispanic/Latino , Not Hispanic/Latino)
- Height (descriptive statistics)
- Weight (descriptive statistics)
- ECOG PS (0, 1, >1)
- Tobacco use (cigarettes, cigars, pipe, chewing tobacco/snuff)

Listing:

- All data listed above by treatment

7.3.3 Baseline Disease Characteristics

Summary:

The following (source CRF) baseline disease characteristics will be summarized for all treated subjects by treatment and overall.

- Disease etiology (Non-viral/HCV/HBV)
- Time from initial diagnosis to treatment (< 1 year, 1-< 2 year, 2 - < 3 year, 3 -< 4 year, 4 - < 5 year, \geq 5 year)
- HCC risk factors (Alcoholic, and others as shown on the CRF)
- Alpha-fetoprotein (AFP) (descriptive statistics)
- AFP category (AFP < 400 ng/ml vs. \geq 400 ng/ml, < 200 ng/ml vs. \geq 200 ng/ml)
- Child-Pugh class (A/B/C) and Score (5 - 15, categorical) (see **Appendix 1** for the details)
- Vascular invasion (VI)
- Extrahepatic spread (EHS)
- VI or EHS
- Sites of diseases (all lesions, target lesions); number of disease sites per subject (all lesions); number of target lesions, non-target lesions and disease sites at baseline; tumor burden: sum of the diameters of target lesions at baseline; number of liver nodules; tumor invasion in liver above 50%

Listing:

- All data above listed by treatment

7.3.4 Physical Measurements

Physical measurements such as body weight, height, body mass index (BMI) and ECOG PS will be listed for all treated subjects.

7.3.5 Medical History

[figure not shown]
General medical history will be listed by subject.

7.3.6 Prior Sorafenib Therapy

A subject is deemed to have prior sorafenib therapy if the subject has at least one record of sorafenib treatment in prior systemic therapy or has been checked “Yes” for the question of “prior HCC medication” on the CRF. Subjects may have multiple records of sorafenib treatments.

The following will be summarized:

- Summary of sorafenib prior treatment (Naïve/Treated/Intolerant)
- Summary of best overall response from sorafenib therapy (All unique sorafenib records per subject)
- Summary of duration of prior sorafenib therapy (All sorafenib records)
- Summary of prior sorafenib therapy setting of regimen (All sorafenib records)
- Summary of time from last sorafenib stop date to start of the study medication
- Summary of primary reason for sorafenib discontinuation (All unique sorafenib discontinuation reasons per subject will be counted)

7.3.8 Pre-treatment Events

Liver, HCC and sorafenib-related pre-treatment events will be summarized by worst CTC grade, system organ class and preferred term. A by-subject listing will be provided.

7.4 Extent of Exposure

The extent of exposure will be characterized according to the number of subjects exposed, the duration of exposure, and the dose to which they were exposed. Analyses in this section will be performed on all treated subjects “as treated”.

7.4.1 Study Therapy

Summary:

Duration of treatment will be presented by treatment using a Kaplan-Meier curve whereby the last dose date will be the event date for those subjects who are off study therapy. Median duration of treatment and associated 95% CI will be provided. Subjects who are still on study therapy will be censored on their last dose date.

Descriptive statistics will be provided by study drug (i.e. BMS-986183, Nivolumab) for the following.

- Number of doses received (summary statistics)
- Duration of therapy (weeks)
- Cumulative dose
- Dose intensity
 - Relative dose intensity (%) using the following categories: <50%; 50 - < 70%; 70 - < 90%; 90 - < 110%; \geq 110%

Error! Reference source not found. summarizes the key parameters used to calculate dosing data for each study.

Table 7.4.1- 1: Study Therapy Parameter Definition

	BMS-986183	Nivolumab
Dosing Schedule per Protocol	At the assigned dose (for Part 1 and 3) or at the recommended dose (for Part 2 and 4) every 21 days	360 mg every 21 days for Part 3 and 4
Dose	Dose (mg) is defined as Total Dose administered (mg) collected on the CRF.	Dose (mg) is defined as Total Dose administered (mg) collected on the CRF.
Cumulative Dose	Cum Dose (mg) is the sum of the doses (mg) administered to a subject during the treatment period.	Cum Dose (mg) is the sum of the doses (mg) administered to a subject during the treatment period.
Dose Intensity	Cum dose (mg)/[(Last dose date ^a - Start dose date + 21)] \times 21	Cum dose (mg)/[(Last dose date ^a - Start dose date + 21)] \times 21
Relative Dose Intensity (%)	Cum dose (mg)/[(Last dose date - Start dose date + 21) \times (planned dose/21)] \times 100	Cum dose (mg)/[(Last dose date - Start dose date + 21) \times (planned dose/21)] \times 100
Duration of Therapy	Last dose date - Start dose date +21.	Last dose date - Start dose date +21

^a Last observed dosing date regardless of retreatment status.

Listing:

- Administration of each study drug
- Duration, cumulative dose, dose intensity and relative dose intensity of each study drug

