Retreatment may be allowed in BMS-986183 and nivolumab dose escalation (Part 3) and BMS-986183 and nivolumab dose expansion (Part 4) of this study for subjects with disease progression during follow-up. Subjects who complete approximately 1 year (17 cycles, with 21 days/cycle) of study therapy and who enter survival follow-up with ongoing disease control (CR, PR, or SD) for reasons other than drug-related toxicity may be eligible for retreatment, upon subsequent confirmed disease progression within 12 months of the last dose of study drug (on a case-by-case basis) after careful evaluation and discussion with the BMS Medical Monitor to determine whether the benefit/risk ratio supports administration of further study therapy. Subjects meeting criteria for retreatment will be treated up to approximately 1 year (17 cycles, with 21 days/cycle) with the originally assigned dose regimen (eg, same dose and dose schedule administered during the first approximately 1 year [17 cycles, with 21 days/cycle]) or modified dose regimen, unless that dose and schedule were subsequently found to exceed the MTD, in which case the subject will be treated at the next lower or alternate dose and schedule. Subjects entering this phase will follow the schedule as outlined in Table 5.1-3. Samples for PK will be collected less frequently (Table 5.5.1-3).

Response Follow-up Period

Subjects with SD, PR, or CR at study drug discontinuation will continue to have radiologic and clinical tumor assessments at least every 3 to 4 months during the survival follow-up period (Section 3.1) until progression, death, or initiation of new treatment (whichever occurs first).

Radiological tumor assessments for subjects who have ongoing clinical benefit may continue to be collected after subjects complete the survival follow-up period of the study. Subjects who have disease progression following treatment with study drug will not be evaluated for response beyond the EOT visit and will be allowed to receive other tumor-directed therapy as required.

3.1.1 Dose Escalation (BMS-986183 Dose Escalation [Part 1] and BMS-986183 and Nivolumab Dose Escalation [Part 3])

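### For retreated Part 3 and 4 subjects, the dose-intensity denominator in SAP Table 7.4.1-1 counts the planned off-treatment gap as dosing time

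*SAP*

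**What the plan says.** SAP 7.4.1 defines the exposure measures in Table 7.4.1-1, identically for BMS-986183 and nivolumab.

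- Dose intensity begins "Cum dose (mg)/[(Last dose date ^a - Start dose date + 21" and is scaled to 21 days. The superscript leads to the table's only footnote: "Last observed dosing date regardless of retreatment status".
- RDI begins "Cum dose (mg)/[(Last dose date - Start dose date + 21", with planned dose per 21 days in the denominator. It carries no marker. It is reported as "Relative dose intensity (%) using the following categories: <50%; 50 - < 70%; 70 - < 90%; 90 - < 110"% and at or above 110%.
- Duration of therapy is the same span in days, again without a marker.
- Cumulative dose is "the sum of the doses (mg) administered to a subject during the treatment period". The table does not say whether retreatment doses belong to that period.
- The nivolumab schedule is "360 mg every 21 days for Part 3 and 4".

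The same section plans a Kaplan-Meier curve of treatment duration, with last dose date as the event date for subjects off therapy. Nothing in SAP 7.4 subtracts an off-treatment interval or reports exposure by course.

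Protocol 3.1 (Retreatment during Survival Follow-up) allows retreatment in Parts 3 and 4 for subjects who completed about 17 cycles and entered follow-up with ongoing disease control. It applies "upon subsequent confirmed disease progression within 12 months of the last dose of study drug" and runs for up to about 17 further cycles.

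**The concern.** Dose intensity and RDI are read as measures of how much of the scheduled dose was delivered. Their denominator should therefore hold only time in which dosing was scheduled. Between the end of the first course and the start of retreatment, the protocol schedules no dose. Counting that time makes a planned treatment-free interval look like omitted or delayed dosing.

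The error runs one way. It can only lower dose intensity, and it falls on subjects who completed a full course and stopped for reasons other than drug-related toxicity. If RDI and duration use the same date, these subjects also drop into lower RDI categories and appear to have been on therapy for longer than they were. A reader of the exposure tables could take this for poor tolerability of the combination.

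**Working it through.** The SAP gives no numerical exposure result to reproduce, so the check applies its formulas to a subject who receives every dose on time at full dose.

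**Inputs**
- Cycle length 21 days; first course 17 cycles; retreatment up to 17 cycles (Protocol 3.1).
- Nivolumab 360 mg every 21 days (SAP Table 7.4.1-1).
- Gap *g*, from last initial dose to first retreatment dose (assumed): 100 days, the length of safety follow-up in Parts 3 and 4; 6 months = 182.625 days; 12 months = 365.25 days, the outer limit in Protocol 3.1. Months are converted at 30.4375 days (SAP section 8).
- Retreatment doses are counted in cumulative dose (assumed). For RDI and duration, last dose date is taken to mean what the footnote says (assumed).

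**Formulas**, with *c* retreatment doses
- Span = 16 × 21 + *g* + 21(*c* − 1) + 21 days.
- Dose intensity = 360 × (17 + *c*) × 21 / span, in mg per 21 days.
- RDI = (17 + *c*) × 21 / span.

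**Baseline check, no retreatment.** Span = 336 + 21 = 357 days. Dose intensity = 360 × 17 × 21 / 357 = 360 mg and RDI = 100%. The formulas are right when there is no gap.

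**With retreatment**

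| Doses | Gap | Span (days) | Dose intensity (mg/21 d) | RDI | RDI category |
|---|---|---|---|---|---|
| 17 + 17 | 100 d | 793 | 324.1 | 714/793 = 90.0% | 90 to <110% |
| 17 + 17 | 6 mo | 875.6 | 293.6 | 714/875.6 = 81.5% | 70 to <90% |
| 17 + 17 | 12 mo | 1058.25 | 242.9 | 714/1058.25 = 67.5% | 50 to <70% |
| 17 + 4 | 100 d | 520 | 305.3 | 441/520 = 84.8% | 70 to <90% |
| 17 + 4 | 6 mo | 602.6 | 263.4 | 441/602.6 = 73.2% | 70 to <90% |
| 17 + 4 | 12 mo | 785.25 | 202.2 | 441/785.25 = 56.2% | 50 to <70% |

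The span exceeds time on treatment by *g* − 21 days: 161.6 days (23 weeks) at 6 months and 344.25 days (49 weeks) at 12 months.

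For 17 + 17 doses, RDI falls below 90% once *g* exceeds 714/0.9 − 714 + 21 = 100.3 days. It falls below 70% once *g* exceeds 714/0.7 − 714 + 21 = 327 days.

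**Other readings of the unmarked RDI row, 17 + 17 doses**
- Initial-course doses over initial-course dates: 357/357 = 100%.
- Initial-course doses over the full span: 357/793 = 45.0% at 100 days; 357/1058.25 = 33.7% at 12 months.
- All 34 doses over initial-course dates: 714/357 = 200%.

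**Gap removed.** 34 × 21 / (357 + 357) = 100%, dose intensity 360 mg, duration 714 days (102 weeks).

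**Part 2 combination extension.** The first combination dose falls 21 to 42 days after the last monotherapy dose (Protocol 3.1.2.1). For 17 + 17 BMS-986183 doses, RDI is 714/714 = 100% to 714/735 = 97.1%, so the effect there is negligible.

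**The case against.** The strongest objection is to scope. The footnote marker sits on the dose-intensity row alone, and a reader might infer that the footnote also governs RDI, duration and the Kaplan-Meier curve. The SAP does not say so. Protocol 3.1 ends the treatment period when the subject is discontinued from study drug. If the unmarked rows use that period for both doses and dates, RDI is 100% and duration is the true first-course length. This stands: for those rows the distortion is conditional. The difficulty is that the table then uses one term with two meanings in adjacent rows, and RDI is no longer dose intensity divided by planned dose. The wording does not settle which reading applies.

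A second objection is that counting the gap is deliberate. SAP 7.5 treats the initial off-treatment period of retreated subjects as on-treatment in the safety analyses, and the person-years in SAP 7.5.6 also run from first dose. That is a rule for attributing safety events. It is not stated in 7.4, and it gives no reason to put unscheduled weeks into a dosing ratio.

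Third, the impact is limited. Retreatment is confined to Parts 3 and 4 (about 21 + 50 = 71 subjects) and needs a completed course, disease control, later confirmed progression and case-by-case discussion. Routine follow-up lasts up to 6 months, so a 12-month gap is an extreme. The administration listing would still show the gap. All of this stands.

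Finally, the glossary (SAP 8.1) shows no entries in the public copy, and the Data Presentation Plan is a separate document. A definition or a by-course table could exist there.

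**Conclusion.** For dose intensity the point holds on the stated rule: the footnote puts the planned gap into the denominator. A retreated subject with 17 + 17 on-time doses would show about 294 mg per 21 days at an assumed 6-month gap and 243 mg at the 12-month limit, against 360 mg.

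For RDI and duration of therapy it holds only if last dose date has the footnote's meaning and retreatment doses count. RDI is then 81.5% and 67.5% instead of 100%, and duration is overstated by 23 and 49 weeks. At about 100 days with a full second course the RDI category does not change.

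Two wider conclusions might be drawn and are not supported. One is that results for the primary objective are compromised. The primary endpoints (Protocol 8.3.1, SAP 4.1) are adverse events, serious adverse events, events leading to discontinuation, deaths and laboratory grade shifts; these exposure measures are descriptive and drive no test, stopping rule or dose decision. The other is that subjects with long disease control would in general look poorly dosed. Only those actually retreated are affected. The documents do not give their number, so no effect on a group median or category count can be calculated.

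**What to change.** In SAP 7.4.1:

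- Define last dose date and treatment period once, for every row of Table 7.4.1-1, and state whether cumulative dose includes retreatment doses.
- Compute duration, cumulative dose, dose intensity and RDI separately for the initial and retreatment courses. If a total is wanted, sum the course durations and omit the gap.
- Apply the same definition to the Kaplan-Meier curve of treatment duration.
- State which planned dose enters RDI when retreatment uses the modified regimen that Protocol 3.1 permits.

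The cost is an edit to the table and footnote plus minor programming. Dosing dates and doses are already collected, so no new data are needed.
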